2 ETHICAL CONSIDERATIONS

2.1 Good Clinical Practice

This study will be conducted in accordance with Good Clinical Practice, as defined by the International Conference on Harmonisation (ICH) and in accordance with the ethical principles underlying European Union Directive 2001/20/EC and the US Code of Federal Regulations, Title 21, Part 50 (21CFR50).

The study will be conducted in compliance with the protocol. The protocol and any amendments and the subject informed consent will receive Institutional Review Board/Independent Ethics Committee (IRB/IEC) approval/favorable opinion prior to initiation of the study.

All potential serious breaches must be reported to BMS immediately. A serious breach is a breach of the conditions and principles of GCP in connection with the study or the protocol, which is likely to affect, to a significant degree, the safety or physical or mental integrity of the subjects of the study or the scientific value of the study.

Personnel involved in conducting this study will be qualified by education, training, and experience to perform their respective tasks.

This study will not use the services of study personnel where sanctions have been invoked or where there has been scientific misconduct or fraud (eg, loss of medical licensure, debarment).

2.2 Institutional Review Board/Independent Ethics Committee

Before study initiation, the investigator must have written and dated approval/favorable opinion from the IRB/IEC for the protocol, consent form, subject recruitment materials (eg, advertisements), and any other written information to be provided to subjects. The investigator or BMS should also provide the IRB/IEC with a copy of the IB or product labeling information to be provided to subjects and any updates.

The investigator or BMS should provide the IRB/IEC with reports, updates and other information (eg, expedited safety reports, amendments, and administrative letters) according to regulatory requirements or institution procedures.

2.3 Informed Consent

Investigators must ensure that subjects are clearly and fully informed about the purpose, potential risks, and other critical issues regarding clinical studies in which they volunteer to participate.

In situations where consent cannot be given to subjects, their legally acceptable representatives (as per country guidelines) are clearly and fully informed about the purpose, potential risks, and other critical issues regarding clinical studies in which the subject volunteers to participate.

BMS will provide the investigator with an appropriate (ie, Global or Local) sample informed consent form(s) (ICF) which will include all elements required by ICH, GCP and applicable regulatory requirements. The sample ICF will adhere to the ethical principles that have their origin in the Declaration of Helsinki.

Investigators must:

```
Revised Protocol No.: 07
Date: 18-Mar-2019
```

- Provide a copy of the consent form(s) and written information about the study in the language in which the subject is most proficient prior to clinical study participation. The language must be non-technical and easily understood.
- Allow time necessary for subject or subject's legally acceptable representative to inquire about the details of the study.
- Obtain an informed consent signed and personally dated by the subject or the subject's legally acceptable representative and by the person who conducted the informed consent discussion.
- Obtain the IRB/IEC's written approval/favorable opinion of the written ICF (s) and any other information to be provided to the subjects, prior to the beginning of the study, and after any revisions are completed for new information.
- If informed consent is initially given by a subject's legally acceptable representative or legal guardian, and the subject subsequently becomes capable of making and communicating his or her informed consent during the study, consent must additionally be obtained from the subject.
- Revise the informed consent whenever important new information becomes available that is relevant to the subject's consent. The investigator, or a person designated by the investigator, should fully inform the subject or the subject's legally acceptable representative or legal guardian, of all pertinent aspects of the study and of any new information relevant to the subject's willingness to continue participation in the study. This communication should be documented.

The confidentiality of records that could identify subjects must be protected, respecting the privacy and confidentiality rules applicable to regulatory requirements, the subjects' signed ICF and, in the US, the subjects' signed Health Insurance Portability and Accountability Act Authorization.

The consent form(s) must also include a statement that BMS and regulatory authorities have direct access to subject records.

The rights, safety, and well-being of the study subjects are the most important considerations and should prevail over interests of science and society.

Minors who are judged to be of an age of reason as determined by local requirements should also give their assent. The assent should be documented based on local regulations.

3 INVESTIGATIONAL PLAN

3.1 Study Design and Duration

This is a Phase 1/2a, open label study to characterize the safety and tolerability of BMS-986158 monotherapy and/or in combination with nivolumab in subjects with advanced solid tumors and hematologic malignancies. The study has two segments: Part 1 (Phase 1 study - dose escalation, with Schedules A, B and C enrolling at different dosing schedules) and Part 2 (Initial Expansion including subjects with a limited set of tumor types followed by Subsequent Expansion including subjects with an expanded set of tumor types) (see Figure 3.1-1). In Part 1, BMS-986158 will be studied as monotherapy, and in Part 2, BMS-986158 will be studied as monotherapy and may be administered in combination with nivolumab depending on available data from the monotherapy-treated subjects.

The planned sample size consists of up to approximately 90 subjects for Part 1 and up to approximately 327 subjects for Part 2 for a total of up to approximately 417 subjects in the entire study.

In Part 1, the continuous dosing Schedule A enrolled first. Each subject in Schedules A, B and C of Part 1 is administered a single dose of BMS-986158 on Cycle 1 Day 1 and no additional doses are administered until Cycle 2 Day 1. For subjects in Schedule A on Cycle 2 Day 1, which must be within approximately 7 days of the Cycle 1 Day 1 dose administration, and on each subsequent cycle, subjects receive QD dosing for 5 consecutive days of each week, followed by a 2-day rest period, on a 28-day cycle. For subjects in Schedule B on Cycle 2 Day 1, which must be within approximately 7 days of the Cycle 1 Day 1 dose administration, and on each subsequent cycle, subjects receive QD dosing for 14 consecutive days, followed by a 7-day rest period, on a 21-day cycle. For subjects in Schedule C on Cycle 2 Day 1, which must be within approximately 7 days of the Cycle 1 Day 1 dose administration, and on each subsequent cycle, subjects receive OD dosing for 7 consecutive days, followed by a 14-day rest period, on a 21-day cycle. Subjects may continue to receive treatment until disease progression, unacceptable AEs or withdrawal of consent.

In Part 2, Schedule A for BMS-986158 administration has been selected for expansion of the 4.5 mg dose, which will be administered for 2 weeks (10 doses) followed by 3.75 mg for the remainder of the treatment period. Adult and adolescent subjects weighing ≥ 40 kg will be administered a flat dose of BMS-986158 (see Section 1.1.13). Using Schedule A with a loading period of 2 weeks at 4.5 mg followed by 3.75 mg for the remainder of the treatment period, BMS-986158 will be tested as monotherapy, initially in a limited set of tumor types (NMC, CRPC, DHL, Non-DC-DLBCL, and TNBC; Initial Expansion), with Subsequent Expansion into additional tumor types upon observing signals of antitumor activity or favorable PD effects in the initial set of tumor types. If combination therapy is pursued, nivolumab will be administered as a flat dose of 480 mg Q4W in adults and BMS-986158 will be administered using Schedule A.

Further dose modification at the subject level is permitted below the dose level of 3.75 mg depending on the observed toxicity and tolerability (see guidelines for dose modification in Section 4.5.2).

Subjects will complete up to 5 study periods (See Figure 3.1-2): Screening (up to 28 days for Part 1 and up to 40 days for Part 2), Treatment (up to 2 years, until disease progression or other protocolspecified criteria), Clinical Follow-up (30 days for BMS-986158 monotherapy and 30 days, 60 days, and 100 days for combination therapy, if pursued), and Survival Follow-up

Only subjects who

have progressive disease after receiving BMS-986158 in combination with nivolumab may have the option to continue treatment with the combination if combination therapy is pursued. Subjects who have progressive disease after receiving BMS-986158 monotherapy will not have the option to continue treatment with BMS-986158 monotherapy or to receive BMS-986158 in combination with nivolumab.

Revised Protocol No.: 07 Date: 18-Mar-2019

.

[figure not shown]
Safety, PK, and efficacy measurements will occur as indicated in Table 5.1-1, Table 5.1-2 Table 5.1-3, Table 5.1-4, Table 5.1-5, and Table 5.1-6. Pre- and on-treatment biopsies will be required for all adult subjects enrolled in Part 2 to allow the assessment of BMS-986158-induced changes in tumor immune infiltration

The overall duration of the study is expected to be approximately 4 years from the time of the first visit of the first subject to the required survival follow-up of the last subject enrolled. Subjects may discontinue treatment due to disease progression, unacceptable AEs, or withdrawal of consent. The Clinical Follow-up visits will occur approximately 30 days (for subjects who receive monotherapy), and 60 days and 100 days (for subjects who may receive combination therapy) after the subject discontinues study treatment. For subjects in PR or CR who discontinue treatment for AEs, tumor assessments will be performed every 12 weeks for the first year then every 6 months for the second year. If a subject discontinues treatment due to an AE, the subject should be seen in Clinical Follow-up every 30 days until the AEs either resolved to baseline or Grade 1, stabilized, or been deemed irreversible. After completing the Clinical Follow-up Period, subjects will continue on to a Survival Follow-up Period.

The end of the

study will occur after the last treated subject completes their Clinical Follow-up, unless a subject discontinues prematurely.

[figure not shown]

Abbreviations: BL = Burkitt's lymphoma; CRPC = castrate-resistant prostate cancer; DHL = double-hit lymphoma; ES = Ewing sarcoma; NEPC = neuroendocrine prostate cancer; NMC = NUT-midline carcinoma; Non-GC-DLBCL = Non-germinal center diffuse large B-cell lymphoma; NSCLC = non-small cell lung cancer; OC = ovarian cancer; RCC = renal cell carcinoma; Res = response; SOC = standard of care; TNBC = triple negative breast cancer; UCS = uterine carcinosarcoma; UM = uveal melanoma.

totality of data obtained from subjects in the Initial Expansion. If combination therapy with nivolumab is pursued, subjects with any listed tumor type will be *Up to 45 subjects will be enrolled in the Initial Expansion. Subsequent enrollment of subjects with an expanded set of tumor types within and across biomarker groups (eg, fusion proteins, BRD amplifications, MYC amplifications, AR amplifications or mutations) as part of the Subsequent Expansion will depend on the eligible.

Revised Protocol No.: 07 Date: 18-Mar-2019

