Nivolumab	100 mg/vial (10 mg/mL)	IP

Study Assessments:

Safety Outcome Measures: AEs will be assessed continuously during the study and for 30 days after the last treatment of BMS-986158 monotherapy and 100 days post discontinuation of combination therapy. AEs will be coded using the most current version of MedDRA and reviewed for potential significance and importance. AEs will be evaluated according to the NCI CTCAE v4.03. Subjects should be followed until all treatment related AEs have recovered to baseline, or are deemed irreversible by the investigator. Safety assessments will be based on medical review of AE reports and the results of vital sign measurements, ECGs, physical examinations, and clinical laboratory tests.

Efficacy Measures: Disease assessment with computed tomography (CT) and/or magnetic resonance imaging (MRI) (solid tumors and lymphoma) or fluorodeoxyglucose - positron emission tomography (hematologic malignancies, when standard of care [SOC]), as appropriate, will be performed at baseline. Disease assessment will occur every 8-9 weeks ± 1 week from the start of study therapy. Disease assessment at other time points may be performed at the discretion of the investigator. Tumor assessments will continue until disease progression or until subjects withdraw from the study. Tumor responses will be determined as defined by RECIST v1.1 criteria for solid tumors. For hematologic malignancies, responses will be based on the Lugano 2014 Classification for Initial Evaluation, Staging, and Response for Hodgkin Lymphoma. For prostate cancers (CRPC and NEPC), responses will be defined based on PCWG3. At the Sponsor's discretion, scans and measurements may be reviewed by independent radiologists using RECIST v1.1, Lugano 2014, or PCWG3 criteria at a later date, or at any time during the study.

Pharmacokinetic Measures: Pharmacokinetic parameters for BMS-986158 (Cmax, Tmax, AUC(TAU), and AUC(0-T); single dose only if data permits: T-HALF, AUC(INF), CLT/F, Vz/F; multiple dose only: Cmin, Ctau, Ctrough, Accumulation Index (AI) and T-HALFeff), will be derived from parent (BMS-986158) and metabolite plasma concentration versus time data. In addition the metabolite to parent ratios adjusted for molecular weight (MR) will be calculated for Cmax, AUC(0-T), AUC(INF) and AUC(TAU).

Sample Size:

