Monitor for Non- Serious Adverse Events										×									See Section 6.2. Non- serious AE will be collected from first dose of study drug until 30 days post discontinuation of dosing. AEs reported during this time period should be followed until resolved to baseline, stabilized or deemed irreversible
Monitor for Serious Adverse Events										×									All SAEs must be collected from the date of subject's written consent until 30 days post discontinuation of dosing or subject's participation in the study if the last scheduled visit occurs at a later time.

On Treatment Outline (CA011001)- Part 1 Escalation - Schedule A - 5 days on / 2 days off dosing **Table 5.1-2:**

On Treatment Outline (CA011001)- Part 1 Escalation - Schedule A - 5 days on / 2 days off dosing schedule	5	Notes		See Section 5.5.		Tumor Assessments should occur every 8 weeks (\pm 7 days) from date of first dose until PD or treatment discontinuation, whichever occurs later. For subjects who have been on study for ≥ 1 year, tumor assessments should occur every 12 weeks (\pm 7 days) until PD or treatment discontinuation.
0 n /	EOT ^a					*X
days		SI (1				
4 - 5	Cycle 4 and beyond (28 days)	1 0				
ule ,	ys)	D 33				
ched	8 Da	D 12				
1 - Sc	Cycle 3 (28 Days)	8 Q				
ation	Cycl	D I				
Iscal		D76				
t 1 F		D 33				
Par		61 A				
-(10	Days)	D 12				×
0110	Cycle 2 (28 Days)	21 0				
(CA		8 G				
tline	C	D 2		X		
t Ou		20				
men		I O				
eatı ule	Cycle 1(7 Days)	D 4				
On Treat schedule		£ (I				
O ¹ sc]	Cycl6 Day	D 7				
)	10				
Table 5.1-2:	Procedure		Sample Collection	Pharmacokinetic (PK) Sampling	Efficacy Assessments	Tumor Assessments ^e

^a Refer to Table 5.1-6 for Clinical Follow-up and Survival Follow-up Periods

^b QTcF assessments ≥450 msec must be confirmed on repeat ECG. ECGs should be recorded after the subject has been supine for at least 5 minutes. Serial time matched ECGs will also occur on specific days and time points.

cal Protocol	-986158
Clinical	

^c For cycle 1 only, assessments may be performed up to 72 hours prior to dosing.

^e Contrast enhanced CT of the chest, CT/MRI of the abdomen, pelvis, and all other known and/or suspected sites of disease (see Section 5.3.1 for further details).

Table 5.1-3:	On Treatment Outline (CA011001) - Part 1 Escalation - Schedule B - 14 days on / 7 days off dosing
	schedule

Procedure	Cycle 1 (7 Days)	s) (s			(21 (21	Cycle 2 (21 Days)					Cycle 3 (21 Days)			Cy Cy (2	Cycle 4 and beyond (21 days)		EOT ^a	

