Monitor for Serious Adverse Events						Х						All SAEs must be collected from the date of subject's written consent until 30 days post discontinuation of dosing or subject's participation in the study if the last scheduled visit occurs at a later time.
Sample Collection												
Pharmacokinetic (PK) Sampling					X							See Section 5.5. Patients who crossover from monotherapy to combination therapy will not be required to provide samples for PK.
Efficacy Assessments												
Tumor Assessments ^g					Х						X*	Turnor Assessments should occur every 8 weeks $(\pm 7 \text{ days})$ from date of first dose until PD or treatment discontinuation, whichever occurs later.

On Treatment & Follow-Up Outline (CA011001)- Part 2 BMS-986158 Monotherapy and/or in **Table 5.1-5:**

On 1 reatment & Follow-Up Outline (CAULIUUL)- Fart 2 BMS-980138 Monotherapy and/or in Combination with Nivolumab Expansion - Schedule A - 5 days on/2 days off dosing schedule		Notes	For participants with CRPC and NEPC, whole body bone scans should also be performed. For participants with TNBC without measurable lesions outside the breast, contrast enhanced MRI of the breasts should also be performed. *EOT if not assessed within the last 9 weeks.
- 5 day	EOT ^a		
lule A	Cycle 3 and beyond (28 Days)	SI (I	
Sched	Cyc ai beyoi Da	1 0	
sion -	(sá	D 22	
Expan	(28 Da	SI (I	
mab F	Cycle 2 (28 Days)	8 G	
Vivolu		1 0	
with N	(sti	D 77	
ation	Cycle 1 (28 Days)	SI (1	
mbin	Cycle 1	8 U	
Combination with 1		1 U	
	Procedure	± 3 days (for all visits except C1D1 and mandatory tumor biopsy)	

nical Protocol	[S-986158
Clinic	BMS-

Table 5.1-5:	On Coi	Treat mbina	tment tion w	& Foll /ith Nř	low-U _l volum	p Outl ab Ex	ine (C. pansio	A011(n - Sc	001)-] Shedul	Part 2 le A -	t BMS- 5 days	On Treatment & Follow-Up Outline (CA011001)- Part 2 BMS-986158 Monotherapy and/or in Combination with Nivolumab Expansion - Schedule A - 5 days on/2 days off dosing schedule
Procedure		ycle 1 (Cycle 1 (28 Days)	(s/	Cy	cle 2 (2	Cycle 2 (28 Days)		Cycle 3 and beyond (28 Days)		EOT ^a	
± 3 days (for all visits except C1D1 and mandatory tumor biopsy)	1 0	8 G	D 12	D 77	I O	D 8	51 A	D 77	D I	SI (1		Notes
Clinical Drug Supplies												
BMS 986158 Administration		Dosing	regimei	Dosing regimen is 5 days on, 2 days off. Refer to Section 4	ys on, 2	days o	ff. Refei	to Sec	tion 4			Those supplied by BMS or sourced by the investigator. Refer to Section 4

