^g Contrast enhanced CT of the chest, CT/MRI of the abdomen, pelvis, and all other known and/or suspected sites of disease. FDG-PET for hematologic malignancies. See Section 5.3.1 for further details. Bone scan for prostate cancer. Note: Patients who crossover from monotherapy to combination therapy will begin at Cycle 1.	atologic
Revised Protocol No.: 07 Date: 18-Mar-2019	125

	Clinical Follow-up	Clinical Follow-up	Clinical Follow-up	Survival Follow-up	
Procedure	30 days (+/- 5 days)	60 days ^a (+/- 5 days)	100 days ^a (+/- 5 days)	every 12 weeks (+/- 2 weeks)	Notes
Safety Assessments					
Physical Examination (PE)	X	Х	X		See Screening notes. Include breast exam if clinically indicated.
Vital Signs	х	Х	Х		Includes body temperature, blood pressure and heart rate
Performance Status (ECOG)	Х	Х	х		ECOG score (se Appendix 5)
Laboratory Tests	Х	Х	Х		See Section 5.3.2 on "Hematology" and "Serum Chemistry" for specific tests to be included.
Thyroid Function Tests ^b	х	Х	Х		To include TSH with reflex testing (free T3 and free T4) if TSH is abnormal b
PSA for CRCP subjects only	Х	Х	х	Х	
Tumor Assessment				X	For the first year of survival follow-up for subjects who do not already have PD. For participants with CRPC and NEPC, whole body bone scans should also be performed. For participants with TNBC without measurable lesions
					outside the breast, contrast enhanced MRI of the breasts should also be performed.
Adverse Event Reporting	orting				
Monitor for non- Serious Adverse Events	Х	Х	Х		Non-serious AEs will be collected starting with the first dose of study medication and through 30 days after discontinuation of dosing for subjects receiving BMS-986158 monotherapy,

Clinical Follow-up and Survival Follow-up Phase Procedural Outline (CA011001) **Table 5.1-6:**

	Clinical Follow-up	Clinical Follow-up	Clinical Follow-up	Survival Follow-up	
Procedure	30 days (+/- 5 days)	60 days ^a (+/- 5 days)	100 days ^a (+/- 5 days)	every 12 weeks (+/- 2 weeks)	Notes
					and through 100 days for subjects receiving combination therapy.
Monitor for Serious Adverse Events	Х	Х	Х		All SAEs must be collected starting at the time a subject signs informed consent and through 30 days after discontinuation of dosing for subjects receiving BMS-986158 monotherapy, and through 100 days for subjects receiving combination therapy.
Sample Collection					
Pharmacokinetic (PK) Sampling	Х		X		See Section 5.5.1; For subjects receiving combination therapy only

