5.4 Efficacy Assessments

5.4.1 Primary Efficacy Assessment

Disease assessment with CT and/or MRI (solid tumors and lymphomas), or FDG-PET (hematologic malignancies, when SOC), or as appropriate, will be performed at baseline. Disease assessment will occur every 8-9 weeks \pm 7 days from the date of first dose. Disease assessment at other time points may be performed if the investigator is concerned about tumor progression. Tumor assessments will continue until there is disease progression (unless treatment beyond progression in which case imaging should continue as per schedule), or until subjects withdraw from the study. Responses will be based on RECIST v1.1 (Appendix 4) for solid tumors. For hematologic malignancies, responses will be based on the Lugano 2014 Classification for Initial Evaluation, Staging, and Response for Hodgkin Lymphoma (Appendix 9). For prostate cancer (NEPC and CRPC), responses will be based on PCWG3 (including PSA assessments; Appendix 12). At the sponsor's discretion, scans and measurements may be reviewed by independent radiologists using RECIST v1.1, Lugano 2014, or PCWG3 criteria at a later date, or at any time during the study.

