- Duration of Response (DOR): defined for a subject with confirmed response as the time between the date of first response and the date of the first objectively documented disease progression (as determined by RECIST v1.1 for solid tumors, Lugano 2014 criteria for hematologic malignancies, or PCWG3 (including PSA assessments) for prostate cancer [CRPC or NEPC]), or death due to any cause, whichever occurs first. For those subjects who remain alive and have not progressed, duration of response will be censored on the date of last tumor assessment. Subjects who started subsequent therapy without a prior reported progression will be censored at the last tumor assessment prior to initiation of the subsequent anticancer therapy. Response duration will only be evaluated in subjects with a BOR of CR or PR.
- PFS: defined as the time from the first dose of study medication to the date of the first objective documentation of tumor progression or death due to any cause. Clinical deterioration in the absence of radiographic evidence is not considered progression for the purpose of determining PFS. Subjects who neither progressed nor died will be censored on the date of their last tumor assessment. Subjects who did not have any on-study tumor assessments will be censored on the date of the first dose of study medication. Subjects who started subsequent therapy without a prior reported progression will be censored at the last tumor assessment prior to initiation of the subsequent anticancer therapy.
- Progression Free Survival Rate (PFSR) at week 't' : defined as the proportion of subjects who remain progression free and surviving at 't' weeks (t=12, 24). The proportion will be calculated by the product-limit method (Kaplan-Meier estimate) which takes into account censored data.

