#### 4.2.1 Preliminary Antitumor Activity

Changes in solid tumor measurements and tumor response will be assessed by the RECIST v1.1 (Response Evaluation Criteria in Solid Tumors version 1.1) (Protocol Appendix 4), or PCWG3 for prostate cancer (Protocol Appendix 12). PCWG3 criteria is intended for Part 2 subjects and not Part 1 subjects. Changes in hematologic malignancies will be assessed using Lugano 2014 criteria (Protocol Appendix 9). In Schedule A (Part 1), tumor assessments will occur 8 weeks ( $\pm 1$  week) after treatment begins and continue every 8 weeks ( $\pm 1$  week) until investigator-assessed disease progression or treatment discontinuation. In Schedules B and C (Part 1), tumor assessments will occur 9 weeks ( $\pm 1$  week) after treatment begins and continue every 9 weeks ( $\pm 1$  week) until investigator-assessed disease progression or treatment discontinuation. In Part 2, Schedule A, tumor assessments will occur 8 weeks ( $\pm 1$  week) after treatment begins and continue every 8 ( $\pm 1$  week) until investigator-assessed disease progression or treatment discontinuation.

The following set of study-level efficacy endpoints will be used.

- Objective Response Rate (ORR): defined as the total number of subjects whose best overall response (BOR) is either a CR or PR divided by the total number of subjects in the population of interest.
  - Best overall response (BOR): defined as the best response designation recorded between the dates of first dose and the date of first objectively documented progression per Investigator assessed RECIST v1.1 (or Lugano 2014 criteria for hematologic malignancies or PCWG3 for prostate cancer) or the date of subsequent therapy, whichever occurs first.

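### The protocol and SAP give incompatible rules for tumor scans after treatment stops without progression, so PFS event and censoring dates depend on which passage a site follows

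*Protocol*

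**What the plan says.** Five statements of the scan rule stand in the current text.

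- **Protocol Section 3.1, repeated in the synopsis and SAP Section 2.1.** "For subjects in PR or CR who discontinue treatment for AEs, tumor assessments will be performed every 12 weeks for the first year", with scans every 6 months in the second year. Subjects with stable disease, and responders who stop for other reasons, are not mentioned.
- **Protocol Table 5.1-6 (follow-up).** Tumor assessment sits in the 12-weekly survival follow-up column with the note "For the first year of survival follow-up for subjects who do not already have PD". There is no second-year row.
- **Protocol Table 5.1-5 (Part 2).** Scans run every 8 weeks "from date of first dose until PD or treatment discontinuation, whichever occurs later". The Part 1 tables use the same end point, every 8 or 9 weeks, but drop the later-of-the-two clause for subjects on study for at least a year.
- **Protocol synopsis and Section 5.4.1.** The synopsis says "Tumor assessments will continue until disease progression or until subjects withdraw from the study"; Section 5.4.1 says "Tumor assessments will continue until there is disease progression".
- **SAP Section 4.2.1.** Scans continue "until investigator-assessed disease progression or treatment discontinuation", without the later-of-the-two clause.

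On analysis, Protocol Section 8.3.2.1 says "Subjects who neither progressed nor died will be censored on the date of their last tumor assessment". SAP Section 4.2.1 does the same at the last evaluable assessment. Both count death from any cause as a PFS event, and neither limits the time since the last scan.

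**The concern.** A subject who stops treatment without PD is scanned to progression, scanned for a year, not provided for, or not scanned, depending on where the site looks. The PFS date comes straight from the scans, so the endpoint inherits the ambiguity. Two effects follow if scanning stops. A subject still alive is censored at the last scan before stopping, and that censoring is tied to tolerability and possibly to prognosis. A subject who later dies becomes an event at death rather than at the earlier, unseen progression, which lengthens PFS. If sites follow different passages, the pooled curve mixes these. A progression that was never scanned for cannot be dated at analysis.

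Response duration, a stated secondary objective, is exposed as well, but only through responders. Their post-treatment follow-up is two years, one year, to PD, or none, depending on the passage. A responder who stops for a reason other than an AE is not covered by Section 3.1.

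**Working it through.** **1. The rules side by side, for a subject who stops without PD**

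| Source | Who | Interval | End |
|---|---|---|---|
| Protocol 3.1, synopsis, SAP 2.1 | PR/CR stopping for AEs | 12 weeks, then 6 months | 2 years |
| Table 5.1-6 | all without PD | 12 weeks | 1 year of survival follow-up |
| Table 5.1-5 | all | 8 weeks | later of PD and stopping, hence PD |
| Synopsis, Protocol 5.4.1 | all | 8 to 9 weeks | PD or study withdrawal |
| SAP 4.2.1 | all | 8 or 9 weeks | PD or stopping |

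**2. One invented Part 2 subject.** Stable disease at week 8, stops for toxicity at week 10, true progression at week 18, death at week 60. Table 5.1-5 asks for an end-of-treatment scan only if none was done in the last 9 weeks; 10 − 8 = 2 weeks, so none is due.

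- Table 5.1-5 and Section 5.4.1: scans at weeks 16 and 24, so PFS event at week 24.
- Table 5.1-6: survival follow-up starts 30 days after stopping (SAP 6.1.2), at 10 + 30/7 = week 14.3. The first scan is at 14.3 + 12 = about week 26, or at 10 + 12 = week 22 if the interval runs from stopping. PFS event at week 22 or about 26.
- SAP 4.2.1: no further scan. PFS event at week 60, or censored at week 8 if the death has not occurred by the analysis.
- Section 3.1: no provision for this subject.

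**3. Illustrative size.** The documents give no PFS assumptions, so all inputs here are assumed: 100,000 simulated subjects per scenario; median time to progression 12 or 20 weeks; toxicity discontinuation by week 24 of 10% or 30%; median 24 weeks from progression to death; discontinuation independent of, or correlated with, progression risk; 8-weekly on-treatment scans; 104 weeks of follow-up. Under the Table 5.1-6 rule, the first off-treatment scan is placed 4 weeks after stopping, then every 12 weeks. Kaplan-Meier PFS at week 24:

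| Rule after stopping | 24-week PFS |
|---|---|
| Scan every 8 weeks to PD (reference) | 25.0% to 49.9% |
| Scan every 12 weeks for one year | +0.7 to +2.7 points |
| No scans, later deaths counted | +1.9 to +8.3 points |
| No scans, deaths not counted, censored at last scan, independent | within 0.1 point |
| Same, correlated | +0.9 to +3.0 points |

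The largest shift is 33.4% − 25.1% = 8.3 points (median 12 weeks, 30% discontinuation, independent). With no scans and no deaths counted, the share of subjects with an observed event falls, for example from 1.00 to 0.75 or from 0.87 to 0.60 at 30% discontinuation.

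**4. Response duration.** The SAP presents it only with more than 5 responders in a tumor type. For 9 subjects, P(at least 6) = Σ C(9,x) pˣ(1−p)⁹⁻ˣ over x = 6 to 9: 0.01% at an ORR of 10%, 5.4% at 35%, and 130/512 = 25.4% at 50%.

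**5. How many subjects.** Protocol Section 1.4.4: 81 treated and 68 stopped for progression at the 21-Dec-2018 cutoff. 81 − 68 = 13; 13/81 = 16%. This is a ceiling, since it includes subjects still on treatment and every other reason for stopping.

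**The case against.** The strongest reply is that the text can largely be harmonised. Section 3.1 does not say that only responders are scanned. It refers efficacy measurements to Tables 5.1-1 to 5.1-6, and Sections 3.5 and 3.7 send discontinued subjects to Section 5. One could therefore read year 1 for everyone without PD and year 2 for responders who stop for AEs. The SAP 4.2.1 sentence can be read as visit timing, since SAP 2.1 itself schedules scans after stopping. The endpoints are descriptive, PFS is not named in the secondary objective, and with 9 subjects sampling error dominates: the exact 95% interval for 3/9 is about 7% to 70%.

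Much of this stands, and it rules out several stronger readings that a reader might infer.

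- That Section 3.1 denies scans to stable-disease subjects: it is silent on them.
- That the SAP censors at treatment stop: its definitions censor at the last evaluable assessment, and earlier only for subsequent therapy.
- That stable-disease subjects distort response duration: they never enter it.
- That PFS becomes progression on drug: death from any cause remains an event.

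The harmonised reading still fails. It does not fit the Table 5.1-5 note, the synopsis, Section 5.4.1 or SAP 4.2.1. The cross-references to Section 5 do not settle the matter, because Tables 5.1-5 and 5.1-6 differ on both interval and end point. The second-year scans of Section 3.1 have no row in Table 5.1-6. The SAP says it will identify substantial differences from the protocol, and it flags none here.

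**Conclusion.** The contradiction is real. It lies mainly within the protocol; the SAP repeats one version and adds another. It concerns a data-collection rule that fixes PFS progression and censoring dates, so it should be settled, although no primary conclusion rests on it.

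If scans stop at discontinuation and later deaths are counted, PFS is biased upward, by 1.9 to 8.3 points at 24 weeks over the assumed grid. If such subjects are only censored, the shift is negligible when toxicity stops are independent of progression risk and up to 3.0 points under the assumed correlation. Those figures show direction and order of size; they are not estimates for this trial. Response duration is affected only through responders and would seldom be reported for a 9-subject cohort.

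A reader might take 13 of 81 as the number affected, or 1/9 (11 points) per subject as the error in a cohort's 24-week PFS. The documents support neither. They give no count of subjects who stopped without PD for toxicity, the 13 come from Part 1 across doses and schedules, and 1/9 is a worst case that ignores Kaplan-Meier handling of censoring. That sites actually differ in practice is possible but not documented. The ORR-based sample size is unaffected.

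**What to change.** Reconcile Protocol Section 3.1, the synopsis, the notes to the on-treatment tables, Table 5.1-6, Section 5.4.1, and SAP Sections 2.1 and 4.2.1 into one assessment rule for every subject who stops treatment without PD, whatever the reason or best response. At a minimum, apply the year-1 12-weekly scans that Table 5.1-6 already schedules. Whether scans go on beyond one year is for the sponsor to decide; Table 5.1-6, Section 3.1 and the Table 5.1-5 note should then agree.

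In SAP 4.2.1, replace the clause that lets treatment discontinuation end scanning with the reconciled rule. State that post-treatment scans before subsequent therapy count toward PFS and response duration, as the SAP censoring definitions already imply.

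The cost is a protocol clarification, a short SAP edit, and some 12-weekly scans at any site now following the narrower Section 3.1 text. Scanning past one year would add to what Table 5.1-6 requires, and that burden belongs in the sponsor's decision.
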